9.2 Presentation of Tables/Listings/Figures (TLFs)

Tables and figures will be sorted by treatment group (in the order stated in Table 6) and chronological time point (where applicable).

Table 6: Treatment Groups and Regimens

Treatment Group	Regimen	Presentation for the PA	Presentation for the LTE analysis (*)
1	Placebo	Placebo	Placebo/Evobrutinib 50 mg BID
2	Evobrutinib 25 mg QD (once daily)	Evobrutinib 25 mg QD	Evobrutinib 25 mg QD/Evobrutinib 50 mg BID
3	Evobrutinib 75 mg QD	Evobrutinib 75 mg QD	Evobrutinib 75 mg QD/Evobrutinib 50 mg BID
4	Evobrutinib 50 mg BID (twice daily)	Evobrutinib 50 mg BID	Evobrutinib 50 mg BID/Evobrutinib 50 mg BID

(*): Subjects who complete the 52-week Double-blind placebo-controlled period will be offered participation in an optional open label, LTE period for an additional 2 years. During this LTE period, subjects will be administered evobrutinib at an initial dose of 50 mg BID or the eventual Phase III dose, when decided.

All data recorded during the trial will be presented in individual data listings (in the order stated in Table 6). All listings are sorted by treatment group, subject, and time point (where applicable), if not otherwise stated.

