14.1.2.3 Supportive Analyses of SRI-4 and SRI-6

The following supportive analysis will be performed for the two-primary endpoints:

Supportive analysis #1: linear trend test

For each of the two-primary endpoints, a test of linear trend in log odds of SRI response with increasing dose, will be based on an appropriate contrast from the logistic model (i.e., (3, 1, -1, -3)). The p-value reported tests the null hypothesis that the log odds of being SRI responder is the same across treatment groups, against the alternative that the log odds increases linearly with increasing treatment group order.

An example of SAS code is available in Appendix 18.9.

Both p-values based on Wald test and Likelihood ratio test will be presented. They will be added in the summary table of logistic regression.

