14.2.2.2 Analysis of Time to first severe BILAG A flare

The time to first severe flare will be analyzed on the mITT Analysis Set using a stratified log rank test with treatment as main effect and stratification variables used in the randomization (race, screening SLEDAI-2K total score and region) as covariates. The one-sided p-values ($\alpha=0.025$) from the stratified log rank test for treatment comparisons vs placebo will be reported. The multiplicity adjustment procedure as outlined in Section 14.1.2.4 will be applied to assess statistical significance.

In addition, a Cox proportional hazards regression model including treatment as factor and the stratification factor at randomization as covariates will be performed. Ties will be handled by replacing the proportional hazards model by the discrete logistic model. The HR together with its 95% CI will be presented as determined by the proportional hazards model. Placebo group will be used as reference group. The assumptions of proportional hazards will be verified graphically (the curves representing the relative risk will be plotted for each treatment group and should be parallel).

KM estimates (product-limit estimates) will be presented by treatment arm together with a summary of associated statistics (median, Q1 and Q3, minimum and maximum) including the corresponding two-sided 95% CI of the median. The KM 5%, 10%, 15% and 20% percentiles as well as the corresponding 95% CI will also be presented. In addition, the number of severe flares by treatment group will be presented.

The KM curves will also be provided for each treatment group.

As sensitivity analyses, stratified log-rank test, Cox model, KM estimates and KM curves will be repeated:

- Using MI as stated in Section 14.2.1,
- On PP analysis set if the size of these analysis sets differs substantially (>10%) from mITT.

In addition, a test for trend in dose-response, using the same Cox model, will be reported as a supportive analysis, using contrast statement and (-3 -1 1 3) coefficients.

An example of SAS code is available in Appendix 18.9.

If there is model convergence problem due to for example zero cells in covariates, appropriate method will be applied to resolve the issue.

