18.9.1 SRI Response

Logistic regression: PROC LOGISTIC with SAS

The logistic regression can be implemented using the following SAS code:

```
proc logistic data=<dataset> descending;
  class TreatmentGroup(ref='Placebo') Region Race SLEDAI_2K_screening;
  model AVALC(event="Y") = TreatmentGroup Region Race
                        SLEDAI_2K_screening / orpvalue clodds=wald;
  ods output CLoddsWald=CLoddsWald;
run;
```

For primary analysis of the 2-primary endpoints and key secondary endpoint *SRI-4 response at Week 52 among serologically active subgroup*, output the 1-sided p-value ($\alpha=0.025$) as below:

- When the OR favors the active treatment (i.e. $OR > 1$), one-sided p-value = two-sided p-value / 2
- When the OR does not favor the active treatment (i.e. $OR \leq 1$), one-sided p-value = 1 – (two-sided p-value / 2)

The interaction can be implemented using the “*” symbol. For example, the following statement takes into consideration the interaction between treatment and region:

```
proc logistic data=<dataset> descending;
  class TreatmentGroup(ref='Placebo') Region Race SLEDAI_2K_screening;
  model AVALC(event="Y") = TreatmentGroup Region Race SLEDAI_2K_screening
                        TreatmentGroup * Region / orpvalue clodds=wald;
  ods output ParameterEstimates=ParameterEstimates CLoddsWald=CLoddsWald;
run;
```

Linear trend in log odds of SRI response for two-primary and key secondary endpoints: PROC LOGISTIC with SAS

In addition to the standard logistic model, the linear trend test can be implemented using the ESTIMATE and CONTRAST statements:

```
proc logistic data=<dataset>;
  class TreatmentGroup Region Race SLEDAI_2K_screening / param=glm;
  model AVALC(event="Y") = TreatmentGroup Region Race
                        SLEDAI_2K_screening;
  ESTIMATE "SRI response rate trend linear in treatment" TreatmentGroup 3 1 -1 -
3;
  CONTRAST "SRI response rate trend linear in treatment" TreatmentGroup 3 1 -1 -3
/ e;
  ods output
  Estimates=Estimates ContrastTest=ContrastTest;
run;
```

Logistic regression subgroup analysis: PROC GLIMMIX with SAS

In addition to the standard logistic model, the subgroup analysis can be implemented using the following code:

```
proc glimmix data=<dataset>;
  class TreatmentGroup (ref='Placebo') SLEDAI_2K_screening;
  model AVALC(event="Y") = TreatmentGroup SLEDAI_2K_screening TreatmentGroup*
  SLEDAI_2K_screening / alpha=0.05 dist=binary;

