    SLEDAI_2K_screening / RL TIES=DISCRETE;
  ods output ParameterEstimates=_es; run;

run;

/*****
STEP 5 : Combined estimates
*****/
/* Combine model coefficients. */
proc sort data=_es;
  by Parameter ClassVal0 _Imputation_;
  run;
proc mianalyze data=_es;
  by Parameter ClassVal0;
  modeleffects Estimate;
  stderr stderr;
  ods output ParameterEstimates = _es_mianal;
run;

/*Exponentiate in order to obtain hazard ratio estimates and confidence intervals */
data resprefix_hr;
  set _es_mianal;
  Log_HR_Comb=Estimate;
```

```
HR_comb=exp(Estimate);  
HR_LCL_comb=exp(LCLMean);  
HR_UCL_comb=exp(UCLMean);  
keep Parameter ClassVal0 Log_HR_comb HR_comb HR_LCL_comb HR_UCL_comb Probt;  
rename Probt=HR_pval_comb;  
run;
```

Logistic regression for the flare-free status

The same procedure as in Appendix 18.9.1 must be applied.

NB model for BILAG A Severe flare / BILAG A or 2B Moderate to Severe flare/ SFI Severe flare

The NB model will be performed using the GENMOD procedure from SAS:

```
proc genmod data=<Dataset>;  
  class TreatmentGroup Region Race SLEDAI_2K_screening;  
  model AVAL = TreatmentGroup Region Race SLEDAI_2K_screening/ alpha=0.05  
  offset=LOGTIME  
  DIST=NB MAXITER=<MaxIter>;  
  ESTIMATE "log flare RR evobrutinib 25mg QD vs placebo" TreatmentGroup -1 1 0 0  
  / EXP;  
  ESTIMATE "log flare RR evobrutinib 75mg QD vs placebo" TreatmentGroup -1 0 1 0  
  / EXP;  
  ESTIMATE "log flare RR evobrutinib 50mg BID vs placebo" TreatmentGroup -1 0 0 1  
  / EXP;  
  ods output estimates=estimates1;  
run;
```

where <maxIter> is the number of iteration (must be sufficiently high to run the model). The offset is equal to the logarithm of years on treatment.

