18.9.3 Other Secondary Endpoints

MMRM model: proc MIXED with SAS

For each continuous endpoint, the MMRM model will be implemented using the MIXED procedure.

A mixed model can be performed with SAS using the following code below. This sample code assumes the treatment group is assigned in the following order:

- 1 = Placebo
- 2 = Evobrutinib 25 mg QD
- 3 = Evobrutinib 75 mg QD
- 4 = Evobrutinib 50 mg BID

The interaction between treatment group and visit must be tested.

```
proc mixed data=<dataset>;
  where avisitn>1;
  class SubjectID Visit TreatmentGroup Region Race SLEDAI_2K_screening;
  model CHG = BASE TreatmentGroup Visit Region Race SLEDAI_2K_screening
  TreatmentGroup*Visit / ddfm=KR s;
  repeated Visit / sub=USUBJID type=UN ;
  lsmeans TreatmentGroup*Visit / pdiff /*e*/ cl;

  %*use estimates or results of PDIFF (DIFFS dataset) but inverse as pdiff
  gives trt=1 minus Trt=2/3/4;

  estimate 'Evobrutinib 25 mg QD - Placebo at W52' TreatmentGroup -1 1 0 0
    TreatmentGroup*Visit 0 0 0 0 0 0 0 0 0 0 0 0 0 0 0 0 0 0 0 0
  0 0 0 0 0 -1 1 0 0 / cl;
  estimate 'Evobrutinib 75 mg QD - Placebo at W52' TreatmentGroup -1 0 1 0
    TreatmentGroup*Visit 0 0 0 0 0 0 0 0 0 0 0 0 0 0 0 0 0 0 0 0
  0 0 0 0 0 -1 0 1 0 / cl;
  estimate 'Evobrutinib 50 mg BID - Placebo at W52' TreatmentGroup -1 0 0 1
    TreatmentGroup*Visit 0 0 0 0 0 0 0 0 0 0 0 0 0 0 0 0 0 0 0 0
  0 0 0 0 0 -1 0 0 1 / cl;  run ;

  ods output lsmeans=lsmeans diffs=diffs Tests3=Tests3;
```

where <TypeMatrix> represents the matrix of covariance (either type=CS or type=UN, see corresponding Section of the IAP for each endpoint). The 0 and 1 for visit and interaction treatment*visit must be adapted, depending on the number of assessments.

Logistic regression with repeated measures: GENMOD procedure from SAS

A logistic model with repeated measures can be implemented using the GENMOD procedure from SAS ® as follows:

```
ods listing close;
proc genmod data=<Dataset> descending;
class USUBJID Visit TreatmentGroup Region;
model AVAL = TreatmentGroup Visit Region TreatmentGroup*Visit / dist=bin
link=logit covb;
repeated subject=USUBJID / type=exch within=Visit;
estimate 'Evobrutinib 25 mg QD - Placebo at W52'
  TreatmentGroup -1 1 0 0
  TreatmentGroup*Visit 0 0 0 0 0 0 0 0 -1 1 0 0 / exp;
estimate 'Evobrutinib 75 mg QD - Placebo at W52'
  TreatmentGroup -1 0 1 0
  TreatmentGroup*Visit 0 0 0 0 0 0 0 0 -1 0 1 0 / exp;
estimate 'Evobrutinib 50 mg BID - Placebo at W52'
  TreatmentGroup -1 0 0 1

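### The SRI linear-trend contrast (3, 1, -1, -3) runs against the alternative it is meant to test, and its sample code does not fix the order of the treatment levels

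*SAP*

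**What the plan says.** SAP 14.1.2.3 plans a linear-trend test for each of the two primary endpoints, "based on an appropriate contrast from the logistic model (i.e., (3, 1, -1, -3". It sets the null of equal log odds across groups "against the alternative that the log odds increases linearly with increasing treatment group order". Wald and likelihood-ratio p-values are both to be shown. The same coefficients stand in Table 17 (two primary endpoints) and in Table 18 (SRI-4 in the serologically active subgroup). The code in 18.9.1 applies them as "TreatmentGroup 3 1 -1 - 3".

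The group order comes from Table 6: placebo, 25 mg QD, 75 mg QD, 50 mg BID. Section 9.2 says: "Tables and figures will be sorted by treatment group (in the order stated in Table 6". Section 18.9.3 repeats that order as codes 1 to 4, but only for the MMRM code: "This sample code assumes the treatment group is assigned in the following order".

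The CLASS statement of the SRI trend code names neither a reference level nor a level order. The main logistic code in the same section has "class TreatmentGroup(ref='Placebo') Region Race SLEDAI_2K_screening".

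For time to first severe flare, 14.2.2.2 plans a trend test "using contrast statement and (-3 -1 1 3) coefficients".

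**The concern.** Two things look wrong.

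1. **Direction.** Read in Table 6 order, the SRI coefficients descend from placebo to the highest dose, while the alternative is ascending. The vector matches the text only if the levels run 50 mg BID, 75 mg QD, 25 mg QD, placebo, and the SAP gives that order nowhere.
2. **Level order.** CONTRAST and ESTIMATE coefficients are applied by position, so their meaning depends on how SAS sorts the levels. The trend code leaves this open. A text variable, or a numeric one carrying a text format, would be sorted by label under the SAS default.

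Table 1 makes dose response part of the primary objective, and this is the only trend test shown for the three SRI endpoints concerned. A wrong sign invites a wrong reading. A wrong level order would change the hypothesis being tested.

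**Working it through.** **Inputs from the SAP.** 103 evaluable subjects per group, placebo SRI-4 rate 40% and a 20-point improvement, so 60% (8.2.1); coefficients (14.1.2.3); group order (Table 6).

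**Assumptions.** Rates at the two middle doses are not in the SAP, so several patterns are used. No covariates; two-sided 0.05. SAS default sorting of CLASS levels by formatted value is software behaviour that the SAP does not state. The figures are for SRI-4 in all subjects.

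**Step 1: which score each group receives**

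| Level order | Placebo | 25 mg QD | 75 mg QD | 50 mg BID |
|---|---|---|---|---|
| Needed for a rising trend | -3 | -1 | 1 | 3 |
| SAP coefficients, Table 6 order | 3 | 1 | -1 | -3 |
| SAP coefficients, alphabetical labels | -3 | 3 | -1 | 1 |

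The correlation with the needed scores is -1 in Table 6 order. In alphabetical order it is (9 - 3 - 1 + 3)/20 = 0.4. The SAP vector is right in neither order.

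**Step 2: size.** z = Σ c·logit(p) / √Σ[c²/(n·p·(1-p))], n = 103; power = Φ(z - 1.96) + Φ(-z - 1.96).

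Rates linear on the logit from 40% to 60% (40, 46.6, 53.4, 60%):
- Needed scores: estimate 2.703, SE 0.898, z = 3.01, two-sided p = 0.0026, upper one-sided p = 0.0013, power 85%.
- SAP scores, Table 6 order: estimate -2.703, z = -3.01, chi-square 9.06, two-sided p = 0.0026, power 85%. The upper one-sided p is 0.9987.
- SAP scores, alphabetical order: estimate 1.081, SE 0.891, z = 1.21, two-sided p = 0.23, power 23%.

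A simulation of 200,000 trials with these rates gave 86% for the needed scores and 23% for alphabetical order.

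Rates 40, 45, 55, 60%:
- Needed scores: z = 3.16, power 88%.
- Alphabetical order: z = 0.92, power 15%.

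Effect at 50 mg BID only (40, 40, 40, 60%):
- Needed scores: z = 2.70, power 77%.
- Alphabetical order: z = 0.90, power 15%.

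Effect at 25 mg QD only (40, 60, 40, 40%), with logit(0.6) = 0.4055 and SE = √[20/(103 × 0.24)] = 0.899:
- Alphabetical order: estimate (3 + 3 + 1 - 1) × 0.4055 = 2.433, z = 2.70, so a 77% chance of a significant positive trend.
- Needed scores: estimate (3 - 1 - 1 - 3) × 0.4055 = -0.811, z = -0.90.

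All three doses at 60%: z = 2.70 and power 77% under both orders, so the misordering costs nothing in that case.

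**The case against.** The best defence of the direction is that the reported p-values do not depend on sign. One-sided testing is reserved for the endpoints in the hierarchical procedure, and this test is outside it. That stands. In Table 6 order the harm is the sign of the estimate and any one-sided reading of the stated alternative. The opposite sign of the flare contrast is not in itself an error either: with placebo first, both contrasts turn negative under benefit, since benefit raises the log odds of response and lowers the log hazard of flare. But 14.1.2.3 states the opposite direction for SRI, and no sign convention is given.

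The level-order problem is conditional. The trend code shows no label. Section 18.9.2 uses control('1') and a numeric-looking treatment macro variable, and 18.9.4 says the treatment variable is usually TRT01AN; all of this points to numeric coding. The code is headed as a sample, and the e option on the CONTRAST statement prints the coefficients, so a check is possible. Against that, ref='Placebo' in the same section and the Pbo and Dose 1 to 3 labels in the tipping-point code point to text or formatted labels. The appendix mixes codings and does not settle which one the trend code uses.

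A reader might also infer that the negative binomial comparisons in 18.9.2 are mislabelled. The documents do not support that: coefficients such as "ESTIMATE 'log flare RR evobrutinib 25mg QD vs placebo' TreatmentGroup -1 1 0 0" fit placebo-first coding exactly. Scores proportional to total daily dose (-2, -1, 1, 2) are likewise a preference. They give 89% power against 88%, and 14.1.2.3 defines the trend by group order, which equal spacing serves.

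**Conclusion.** The contrast is wrong as written: it contradicts its own stated alternative in the only treatment order the SAP defines. That half rests on the text alone. Its effect is a reversed sign, with two-sided Wald and likelihood-ratio p-values unchanged.

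The loss of power from about 85-88% to 15-23% arises only if the treatment variable is sorted by text label, and only under the assumed graded rates. A reader might take the two failures as occurring together. They cannot: reversal needs placebo-first order, and scrambling needs label order.

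Nor do the documents support calling this the only model-based assessment of dose, because 14.1.2.1 gives a model-based odds ratio for every dose against placebo. It is the only trend test shown for these SRI endpoints. It is supportive and outside the multiplicity procedure, so primary and key secondary conclusions are unaffected.

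**What to change.** - Replace (3, 1, -1, -3) with (-3, -1, 1, 3) in 14.1.2.3, Table 17, Table 18 and the trend code in 18.9.1.
- In the SRI trend code (18.9.1) and the flare trend code (18.9.2), use the numeric treatment variable (1 = placebo, 2 = 25 mg QD, 3 = 75 mg QD, 4 = 50 mg BID) with ORDER=INTERNAL, so that a text format cannot change the order.
- State that a positive SRI estimate and a negative flare estimate both mean benefit increasing with dose.

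The flare coefficients can stay as they are. The cost is a few words of SAP text and one CLASS option in the code; no new data are needed. If the trend outputs have already been produced, the coefficients printed by the e option will show which level order was used and whether a rerun is needed.

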3. Whether there was no new BILAG A organ domain scores and ≤ 1 new BILAG B organ domain score compared to Day 1 will be considered as a dichotomic response with value 1 when it is met and 0 otherwise. This score will be imputed using SAS MI procedure (including 2 other components: SLEDAI-2K change from baseline and PGA score) and the response will be deducted from the logic below:
 - i. Values < 0.5 will be imputed as 0,
 - ii. Values > 0.5 will be imputed as 1.

Components no. 1 to 3 will be imputed assuming a MAR pattern. The SAS MI procedure will be performed as follows:

- Monotone missing data structure will be created as follows: intermediate (non-monotone) missing data will be multiply imputed using the Markov chain Monte Carlo (MCMC) method and assuming MAR and multivariate normality. The SAS procedure PROC MI with the MCMC option will be used with seed number = 2005270018. The number of burn-in iterations will be set to 200, which is the default value. Nevertheless, if diagnosis plots show that the convergence has not yet occurred, this will be adjusted.
- Then, each component will be imputed with treatment group, race, region, SLEDAI-2K total score (<10 ; ≥ 10) and data at previous visit from all SRI components as covariates.

- Imputation will be repeated 1000 times. The SRI response will then be calculated for each of the multiply imputed data sets from the imputed components. For this analysis, the estimated OR, together with associated two-sided 95% CI of the estimated OR and nominal p-value from the logistic regression model, comparing each evobrutinib treatment group to placebo will be presented. Results will be combined using MIANALYZE SAS procedure with the Rubin's rules as described in Appendix 18.9.

The SAS code to implement the MI and MIANALYZE procedures is in Appendix 18.9.

The same analysis method as the primary analysis of the two-primary endpoints will be performed using the mITT Analysis Set for SRI-4 and in the HDA subject subgroup for SRI-6.

In addition, the number and percentage of SRI-4/SRI-6 responders and non-responders at Week 52 in each treatment group will be presented the same way as for the primary analysis (see Section 14.1.2.10) using Rubin's rules to gather binomial proportion by each treatment (see Appendix 18.9).

Sensitivity Analysis #3: Tipping Point Analysis

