For this analysis, a subject will be considered as an SRI-4 or SRI-6 Non-Responder if the subject takes EAC-determined protocol-prohibited medications during the treatment period (i.e. EAC-treatment failure).

Tipping point analysis will be performed as in Yan 2009, Section 2.3.2.

All possible combinations of success/failure may be posited in the 4 treatments groups. Results are obtained by a random single imputation of possible scenarios (responder or non-responder) to each arm. All possible combinations of imputations of response among subjects with missing response in the placebo group and evobrutinib 25 mg QD, 75 mg QD and 50 mg BID groups. For each combination, the imputed data were combined with the data from subjects with non-missing data and primary analysis.

Assumptions of missing data due to a missing response at Week 52 will be varied to see if there are any tipping points:

Let

$n_1 =$ number of responders out of missing data due to various reasons for placebo

$n_2 =$ number of responders out of missing data due to various reasons for evobrutinib 25 mg QD

$n_3 =$ number of responders out of missing data due to various reasons for evobrutinib 75 mg QD

$n_4 =$ number of responders out of missing data due to various reasons for evobrutinib 50 mg BID

The same analysis method as the primary analysis of the two-primary endpoints will be performed using the mITT Analysis Set for each possible combination of n_1 , n_2 , n_3 and n_4 .

The values of n_1 , n_2 , n_3 and n_4 where the study result will be tipped from statistically significant (not statistically significant) to not statistically significant (statistically significant) will be assessed for plausibility based on the corresponding response rate from each treatment. See Section 14.1.2.4 for the multiplicity adjustment procedure.

Sensitivity Analysis #4: Unadjusted Analysis

The analysis of the two-primary endpoints will be performed on the mITT Analysis Set.

In this analysis, the logistic regression model will be used with only treatment as a factor.

For this analysis, the estimated OR, together with associated two-sided 95% CI of the estimated OR and nominal p-value from the logistic regression model, comparing each evobrutinib treatment group to placebo will be presented.

In addition, the number and percentage of SRI-4/SRI-6 responders and non-responders at Week 52 in each treatment group will be presented the same way as for the primary analysis (see Section 14.1.2.1).

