- Monotone missing data structure will be created as follows: intermediate (non-monotone) missing data will be multiply imputed using the Markov chain Monte Carlo (MCMC) method and assuming MAR and multivariate log normality. The SAS procedure PROC MI with the MCMC option will be used with seed number = 2005270018. The number of burn-in iterations will be set to 200, which is the default value. Nevertheless, if diagnosis plots show that the convergence has not yet occurred, this will be adjusted.
- Then the response (Severe BILAG A: Yes/No) will be imputed with treatment group, race, region, SLEDAI-2K total score (<10; >=10) and response at previous visit covariates.
- Imputation will be repeated 1000 times. Then depending of the visit of censored observation or of response, the time to first severe BILAG A flare will be computed as described for the non- sensitivity analysis. Estimate and associated standard error of Cox regression analysis applied on each imputed sample will be combined using MIANALYZE SAS procedure with the Rubin’s rules as described in Appendix 18.9.

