PROC MIANALYZE DATA=lgsodds_t;
  MODELEFFECTS log_or_lr_value;
  STDERR log_or_lr_se;
  ODS OUTPUT PARAMETERESTIMATES=mian_lgsodds_t;
QUIT;
*** Back-transform combined values;
DATA mian_lgsodds_bt;
  SET mian_lgsodds_t;
  estimate_back = EXP(ESTIMATE); *Pooled odds ratio;
  qn=quantile('NORMAL',.975);
  LCL_back=Estimate_back*EXP(-qn*STDERR); *Pooled lower limit;
  UCL_back=Estimate_back*EXP(+qn*STDERR); *Pooled upper limit;
RUN;

/*****
STEP 4b : Pooling p-value
*****/
PROC MIANLYZE PARMs (CLASSVAR=CLASSVAL)=ParameterEstimatesMI
  CLASS TreatmentGroup;
  MODELEFFECTS TreatmentGroup;
  ODS OUTPUT PARAMETERESTIMATES=mian_logres
QUIT;
```

Then Step 4a and 4b are to be repeated for the analysis of SRI-6.

Pooling binomial proportion in each treatment arm after MI

```
*** Estimate proportions of responders in each treatment arm;
PROC FREQ DATA=datain_mi;
  TABLES resp / cl binomial(level=2);
```

```
Exact binomial;
BY _Imputation_ TreatmentGroup;
ODS OUTPUT BINOMIALPROP=prop;
RUN;
*** From ODS output dataset BINOMIALPROP, create a dataset
containing estimated proportion of responders in each
treatment arm and their standard errors;
DATA prop_trt;
MERGE
prop(WHERE=(Label1="Proportion")
KEEP=_Imputation_ TreatmentGroup nValue1 Label1
RENAME=(nValue1=prop))
prop(WHERE=(Label1="95% Lower Conf Limit")
RENAME=(nValue1=LOWERCL)
prop(WHERE=(Label1="95% Upper Conf Limit")
RENAME=(nValue1=UPPERCL)
qn = Quantile('NORMAL',.975)
prop_se = (UPPERCL - LOWERCL) / (2 * qn)
BY _Imputation_ TreatmentGroup;
RUN;
*** Combine proportion estimates;
PROC SORT DATA=prop_trt; BY TreatmentGroup _Imputation_; RUN;
PROC MIANALYZE DATA=prop_trt;
MODELEFFECTS prop;
STDERR prop_se;
BY TreatmentGroup;
ODS OUTPUT PARAMETERESTIMATES=mian_prop_trt;
RUN;
```

Tipping point sensitivity analysis

*1- Start by computing the number of missing response in each treatment at the willing visit in macrovariables: nmisspbo nmissd1 nmissd2 nmissd3.

*2- Then complete the tipping point analysis:

```
***TIPPING POINT ANALYSIS FOR BINARY DATA;
data resptip
  set resp;
  if TreatmentGroup='Pbo' then trtn=1;
  else if TreatmentGroup='Dose 1' then trtn=2;
  else if TreatmentGroup='Dose 2' then trtn=3;
  else if TreatmentGroup='Dose 3' then trtn=4;
  randnum=ranuni(200527);
  misspbo=&nmisspbo;
  missd1=&nmissd1;
  missd2=&nmissd2;
  missd3=&nmissd3;
run;
***Sort by random number allow cumulative imputation of failure /
success to subjects in random order;
PROC SORT data=resptip; BY randnum; QUIT;

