DATA resptip2
  SET resptip;
  WHERE trtn in (1 2 3 4);
  ARRAY randcount(4);
  ARRAY t(4);
  *Each missing data will be identified by its number starting from 1, by each
treatment;
  RETAIN randcount 0;
```

```
newresp=resp;
IF resp=. THEN randcount(trtn)+1;
*Output misspbo*missd1 + misspbo*missd2 + misspbo*missd3 scenarios, ie all possible
combination of pbo with the dose;
DO t1=1 to misspbo
  DO t2=1 TO missd1;
  DO t3=1 TO missd2;
  DO t4=1 TO missd3;
  IF resp=. THEN DO;
    IF randcount(trtn)<=t(trtn) THEN newresp=1;
    ELSE newresp=0;
    OUTPUT;
  END;
  ELSE OUTPUT;
END;
END;
END;
END;
```

*3- Then apply primary analysis to the new dataset according to each tipping point scenarios (ie by t1 t2 t3 t4).

From that we could plot p-value of each dose versus pbo.

Looking at t1 vs t2 for the p-value of dose 1.

Looking at t1 vs t3 for the p-value of dose 2.

Looking at t1 vs t4 for the p-value of dose 4.

*Label variable in result dataset that will be displayed in plot;

```
data p;
set pvalue;
label pvalue="P-value"
  t1='N of responders among missing - Placebo'
  t2='N of responders among missing - Dose 1;
  t3='N of responders among missing - Dose 2;
  t4='N of responders among missing - Dose 3;
run;
*Select scenarios and treatment to plot;
%macro selscenartrt (scenarios=, trtnum=,out=)
  data &out.;
  set p;
  where bygroup in (&scenarios) and trtn in (&trtnum.)
%mend selscenartrt;
%selscenartrt (scenarios=%str("t1" "t2"), trtnum=%str(1 2),out=pt1t2)
%selscenartrt (scenarios=%str("t1" "t3"), trtnum=%str(1 3),out=pt1t3)
%selscenartrt (scenarios=%str("t1" "t4"), trtnum=%str(1 4),out=pt1t4)
```

*Plot the wanted comparison;

```
proc sort data=pt1t2;
  by t1 t2;
quit;
proc sgplot data=p;
  title1 "Adjusted p-value 1-side : Placebo vs Dose 1";
  heatmapparm x=t2 y=t1 colorresponse=pvalue / colormodel=TwoColorRamp discretex
discretex transparency=0.2 OUTLINE outlineattrs=(thickness=0.5pt color=gray);
  text x=j y=i text=nvalue2 / textattrs=(size=5pt) strip;
  gradlegend;
```

```
footnote1 justify=left "Placebo: N (ITTm) = xxx1, Observed Resp = xxresp1, Observed  
Non-Resp = xxnresp1 and Missing = &nmisspbo.";  
footnote2 justify=left "Dose 1: N (ITTm) = xxx2, Observed Resp = xxresp2,  
Observed Non-Resp = xxnresp2, Missing = &nmissd1.";  
run;
```

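### The sample code for the two missing-data sensitivity analyses of SRI response departs from the method text: the pooled MI p-value can have the wrong comparator, and the tipping-point grid leaves out zero responders

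*SAP*

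**What the plan says.** **Method text.** For the MI analysis (Sensitivity Analysis #2), SAP Section 14.1.2.2 says that the odds ratio, its 95% CI and a nominal p-value, "comparing each evobrutinib treatment group to placebo will be presented". For the tipping-point analysis (#3) it says "All possible combinations of success/failure may be posited in the 4 treatments groups". Section 14.1.2.1 scores a missing Week 52 response as non-response in the primary analysis.

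**Code, Appendix 18.9.1.**
- The logistic model has "class TreatmentGroup(ref='Placebo') Region Race SLEDAI_2K_screening" with no `PARAM=` option. The trend test in the same section does state its coding: "class TreatmentGroup Region Race SLEDAI_2K_screening / param=glm".
- The interaction example writes two separate tables: "ods output ParameterEstimates=ParameterEstimates CLoddsWald=CLoddsWald". The primary model outputs only the odds-ratio table.
- Step 4a pools log odds ratios. Step 4b pools the p-value from coefficients: "PROC MIANLYZE PARMs (CLASSVAR=CLASSVAL)=ParameterEstimatesMI".
- The placebo tipping loop is "DO t1=1 to misspbo", and the three dose loops also start at 1.

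**Flare imputation.** Section 14.2.1 fills intermittent gaps in a yes/no severe-flare variable by MCMC, "assuming MAR and multivariate log normality". The code in Appendix 18.9.2 then lists the same variables as CLASS variables for a monotone logistic step.

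**The concern.** According to Table 17, Sensitivities 1, 4 and 5 handle missing responses exactly as the primary analysis does. Section 7 drops the completers analysis and reports that drop-out may be higher than expected. Only Sensitivities 2 and 3 therefore vary the missing-data assumption for the two primary endpoints.

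If the code is followed as printed, one row of the MI table could carry an odds ratio for one contrast and a p-value for another. The tipping-point display would also lack its natural starting point and its most adverse corner. A reader could then see fragility or robustness that is not in the data.

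**Working it through.** **Reference point.** Section 8.2.1 gives 103 evaluable per arm, SRI-4 rates of 40% against 60%, a one-sided 0.0125 test per endpoint and 80% power to win on either endpoint. A two-proportion calculation gives 74.0% for SRI-4 and 63.2% for SRI-6 in the high-disease-activity half (30% against 55%, 51.5 per arm). With an assumed correlation of 0.7, the chance of at least one win is 80.5%, or 76.3% if the SRI-6 gain is 20 points. These match the SAP's 80% and 76%. The finding does not rest on them; they only supply realistic inputs.

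**1. Comparator in Step 4b.** Take 41/103 responders on placebo and 62/103 on each dose, with complete data and no covariates. Each arm's log odds has variance v = 1/41 + 1/62 = 0.0405.
- Against placebo: log OR = 2 × ln(62/41) = 0.827; SE = √(2v) = 0.285; z = 2.91; two-sided p = 0.0037.
- Effect-coded coefficient: arm weights −¼, −¼, −¼, +¾; estimate = 0.827/4 = 0.207; SE = √(0.75v) = 0.174; z = 1.19; p = 0.236.

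Other patterns, 103 per arm. The order is placebo, 25 mg QD, 75 mg QD, 50 mg BID. The last column comes from 20,000 simulated trials and is the chance that 50 mg BID reaches one-sided p < 0.025.

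| Rates | 50 mg BID vs placebo, p | Effect-coded p | Chance of significance, placebo / effect-coded |
|---|---|---|---|
| 0.40/0.60/0.60/0.60 | 0.0037 | 0.236 | 81% / 21% |
| 0.40/0.50/0.55/0.60 | 0.0037 | 0.041 | 81% / 54% |
| 0.40/0.40/0.40/0.60 | 0.0037 | 0.0004 | 81% / 95% |
| 0.50/0.30/0.30/0.50 | 1.00 | 0.013 | 2% / 69% |

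The error can go either way. In the second row, the 75 mg QD p-value also moves, from 0.026 to 0.365.

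**2. Step 4a has no BY statement for dose.** As printed, the three dose log odds ratios from 1,000 imputations are read as 3 × 1,000 = 3,000 imputations of one quantity. For rates 0.40/0.50/0.55/0.60 the log odds ratios are 0.405, 0.606 and 0.811 (ORs 1.50, 1.83, 2.25). Their mean is 0.607, which gives a single OR of 1.84.

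**3. Tipping grid.** With m missing in each arm, a dose-placebo pair has (m+1)² scenarios, and the code visits m². The SAP gives no counts, so m is assumed.

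| m | Full | Coded | Omitted |
|---|---|---|---|
| 5 | 36 | 25 | 30.6% |
| 10 | 121 | 100 | 17.4% |
| 20 | 441 | 400 | 9.3% |
| 30 | 961 | 900 | 6.3% |

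The omitted cells always include (0,0), which is the primary analysis, and (m,0), with all missing placebo subjects responding and none on the dose.

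Example with m = 5 and observed responders 41 and 60 of 103: the only non-significant scenario of the 36 is (5,0). There, 46/103 against 60/103 gives one-sided p = 0.026. The worst coded scenario, (5,1), gives 0.019, so the coded 25 show no tipping point.

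Every OUTPUT statement sits inside the nested loops, so an arm with no missing response would leave the whole dataset empty.

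**4. Flare imputation, by reading only.** The logarithm of 0 is undefined, so log normality cannot describe a 0/1 variable. The code has no log transform, so that part is a fault of wording. It also has no rounding step between the MCMC fill and the CLASS statement, so fractional values would become separate class levels. The SRI imputation has a 0.5 cut for its BILAG component; the flare imputation has none.

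**The case against.** The strongest reply is that this is sample code. Appendix 18.9 is titled so and uses permissive wording. The code cannot run as printed: a procedure name is misspelled and the variable list contains prose. A programmer would have to rewrite it, and the method text is sound. In part this stands, and the code should not be called fixed. But the introduction to Appendix 18.9 says it details the implementation, Section 14.1.2.2 sends the reader there for the MI code, and no other rule for pooling the p-value is given.

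Second, no code creates the table that Step 4b reads. Step 4a filters on an effect name containing TRT, which would not match the printed variable name, so the MI model may not be the printed call. This stands as a condition on the first part.

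Third, a p-value at odds with its own CI would be noticed. That is true when all doses work equally. It is not true when only the top dose works, where 0.0037 and 0.0004 agree in direction and the mismatch stays hidden.

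Fourth, the omitted primary point is reported elsewhere, and at 15 or 25 missing per arm a tipping boundary, where one exists, was usually still visible in the coded grid. This stands and limits the size of the tipping fault. Finally, the MI p-values are nominal and do not enter the hierarchy in Section 14.1.2.4.

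**Conclusion.** The concern holds as a departure of the sample code from the method text, with three parts.
- If the Step 4b table comes from the model as shown, and SAS applies its default effect coding, the nominal MI p-value compares each dose with the four-arm mean. It can then disagree in either direction with an OR and CI built on placebo comparisons. Step 4a separately needs dose-wise processing. The p-values above are from complete, unadjusted data and illustrate the contrast; they do not predict the MI result.
- The tipping grid loses its zero row and column, contrary to the text. The loss is material when few responses are missing and modest when many are.
- The flare imputation is a smaller point, concerning a key secondary endpoint.

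A reader might infer that neither sensitivity analysis tests the primary result. The documents do not support that. Step 4a draws on odds ratios against placebo, so only the MI p-value has the wrong comparator. The tipping analysis applies the primary model validly in every scenario it visits. The primary p-values come from the odds-ratio table and are unaffected.

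**What to change.** - **Step 4a:** sort and process by dose, and take the OR, CI and p-value from the pooled log odds ratio. If Step 4b is kept instead for the p-value, set `PARAM=REF` with placebo as reference in the model that feeds it, and show the step that creates its input. Step 4a needs dose-wise processing in either case, because the OR and CI come from it.
- **Tipping point:** start all four loops at 0, and correct the scenario count in the code comment.
- **Flare imputation:** remove the log-normality wording. Either set intermittent values to 0/1 before the monotone logistic step or use FCS LOGISTIC.
- **Production programs:** check whether they followed the sample code, and rerun any affected sensitivity outputs.

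The edits are a few lines and need no new data. Version 4.0 of the plan postdates the review of the primary analysis (Sections 6.3 and 6.4), so the real cost is limited reprogramming and a possible rerun of sensitivity outputs already produced.
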